
Statistical Analysis Plans for Each Aim Study Duration	to the placebo TE2 condition. Irritability symptoms will be measured daily using the III temper subscale of the Inventory of Depression and Anxiety Symptoms. Theta and Beta oscillatory frequencies will be assessed at rest and in response to the Dot Probe task and the Affective Posner Paradigm administered at the last day of each condition. Urinary measures of E1G will be collected every day during the last week of each condition and measured using an enzyme immunoassay (Arbor Assays, Ann Arbor, MI), with sensitivity at < 22.5 pg/mL to generate to within subject variability in E1G (indexed by the standard deviation of E1G). Aim 1 Plans. Linear regression models will predict irritability symptoms and theta and beta frequencies in response to tasks from E1G variability (based on the standard deviation of seven daily E1G measurements) and predict irritability symptoms from theta and beta task-related frequencies. Aim 2 Plans. The two repeated post-treatment EEG measures (theta and beta task-related frequencies) will be modeled as a function of fixed factors including baseline EEG measures (continuous), Condition status (TE2 or placebo; binary), and order of Condition (binary) in a linear mixed effects model with a random intercept accounting for the within-subject variance. The two-sided Wald test will test the significance of TE2 effects. 2b) Similarly, daily irritability symptoms (3 weeks/Condition) will be modeled as a function of fixed factors including baseline irritability symptoms (continuous), Condition, and order of Condition in a linear mixed effects model with a random intercept accounting for within-subject variance.
Participation Duration	Sixteen weeks
Enrollment Duration	Two years

2. Introduction

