Define the baseline relationships between: (a) E1G variability and irritability symptom severity; (b) E1G variability and theta and beta oscillatory correlates of threat and frustration; (c) irritability symptoms and theta and beta oscillatory correlates of threat and frustration. The estimands of interest are the correlation coefficients between a) E1G variability (standard deviation (SD) of E1G over the four-week baseline phase) and irritability symptoms b) E1G variability (SD) and theta and beta oscillatory activation during threat and frustration tasks; and c) irritability symptoms and theta and beta oscillatory activation during threat and frustration tasks.

3.2. Aim 2

Determine whether TE2, versus placebo, will: a) beneficially modify task-evoked theta and beta oscillations (i.e., reduce theta and increase beta activation) in response to threat and frustration tasks; and b) reduce irritability symptom severity. The estimands of interest are a) the mean difference (and direction of difference) between the active TE2 and placebo TE2 conditions in theta and beta activation to threat and frustration tasks and b) the mean difference (and direction of difference) between the active TE2 and placebo TE2 conditions in mean irritability symptom severity.

4. Study Design

This single site, interventional study employs a within-subjects, cross-over, placebo-controlled, double-blind design.

Stage 1: A four-week baseline assessment involving: 1) at home urine collections of E1G; 2) mood ratings (general mood and irritability specific ratings); and 3) in-lab EEG session to assess theta and beta oscillations in response to behavioral tasks designed to elicit threat reactivity (Dot Probe task) and frustration to non-reward (Affective Posner Paradigm). Four weeks was chosen to allow for a sufficient number of E1G collections (n=14) to calculate a reliable standard deviation score for each participant.

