Stage 2: Participants are randomized (1:1) to either three weeks of transdermal E2 (0.1 mg/day) or to three weeks of transdermal placebo as their first condition (Condition 1), followed by a three-week washout period and then exposed to Condition 2 (three weeks transdermal placebo if Condition 1 was active TE2 or three weeks of was active TE2 if Condition 1 was transdermal placebo). Daily irritability ratings and weekly irritability and general mood ratings are collected throughout all conditions in Stage 2. Daily urinary E1G is sampled in the last week of Condition 1 and Condition 2. Laboratory EEG sessions occur at the end of Condition 1 and Condition 2 to assess theta and beta oscillatory activity in response to behavioral tasks designed to elicit threat reactivity (Dot Probe task) and

We have chosen 3 week duration for each Condition based on: 1) Preliminary results of [name] showing maximal effect of TE2 on irritability symptoms within one week; 2) placebo-controlled studies showing TE2 reduces perimenopausal depression symptoms with maximal effects seen in one to three weeks;^{27,28} 3) withdrawal from TE2 increases depressive symptoms within one week in perimenopausal women with histories of perimenopausal depression;²⁹ and 4) clinical experience that maximal efficacy of TE2 for treating perimenopausal depression is evident within two weeks (personal communication, [name]). Thus, the beneficial mood effects of TE2 are rapid and detectable within 3-weeks. With the mean half-life of TE2 equal to 161 mins,³⁰ pharmacokinetic clearance is complete in 13 hours (five half-lives). We will employ a three-week washout window to minimize, if not eliminate, even lagged carryover effects³¹

Stage 3: Participants will be given, in an unblinded fashion, 200 mg Prometrium for ten days to induce a menstrual bleed in order to prevent thickening of the endometrium in response to TE2. Participants will be followed for 3-4 weeks to document onset, duration, and magnitude of the menstrual bleed. A progestin every 2-3 months is sufficient for endometrial protection,²⁴ particularly in women in the early menopause transition who are still menstruating, albeit irregularly.

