4.3. Measurement Design

Table 1. Variables of interest: their occasions of evaluation, their uses for the aims, their roles in the study

Variables within Domains	Scale ¹	Visits ²	Aims	Main Roles
Identifiers				
Participant ID	nominal	all	all	identifier
Screening Profile				
systolic blood pressure (SBP)	mmHg	0, 5-7, 11-13	N/A	screening and safety
diastolic blood pressure (DBP)	mmHg	0, 5-7, 11–13	N/A	screening and safety

body mass index (BMI)	kg/cm ²	0, 7, 13	N/A	screening and safety
age	decimal yrs	0	N/A	screening
Life Events Survey	binary	0	N/A	screening
Psychiatric history	categorical	0	N/A	screening
Medical and cancer history	binary	0	N/A	screening
Reproductive Stage	binary	0	all	screening
Research Lab Assays				
Urinary E1G	pg/ml	1-4, 7, 13	Aim 1	predictor
EEG (theta and beta) oscillatory activation	dB	4, 7, 13	all	primary outcome
Patient-Reported Outcomes				
Daily self-reported irritability	continuous	1 – 13	all	primary outcome
Behavioral inhibition/Activation Scale (BIS/BAS)	continuous	4, 7, 13	Aim 2	secondary outcome
Frustration to non-Reward Scale	continuous	4, 7, 13	Aim 2	secondary outcome
Green Climacteric Scale	continuous	0, 4, 7, 13	all	covariate
Pittsburgh Sleep Quality Index	continuous	0, 4, 7,13	all	covariate
Safety Monitoring				
AEs and SAEs documentation	events	0, 4-13	N/A	safety monitoring

¹Units of measurement or the scale.

Screening Measures:

Blood pressure will be taken at baseline to confirm eligibility (< 160/100 mmHg) based on a minimum of three stethoscopic blood pressures taken by a trained research staff member. Participants will be seated comfortably for a minimum of five minutes prior to the first reading with arm supported on a table. Assessments will be at least one minute apart. A mean systolic and diastolic pressure (SBP and DBP) will be derived based on the three readings. Participants must have a resting SBP <160 and a resting DBP <100 mmHg to continue in the research. The same BP protocol will be used at study visit 5-7 and 11-13 to ensure the participant remains normotensive.

Body Mass Index will be derived based on height and weight measured by a research assistant in the laboratory using the Health-o-meter (Professional) scale. BMI will be calculated using the formula: weight in kg/height in m²

Age will be determined by self-report.

Reproductive Stage will be initially determined by phone and confirmed in the enrollment session based on self-report of bleeding patterns.

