7.8. Early Discontinuations

Data to be Collected

If a participant chooses to withdraw consent or discontinue with the study interventions no medical records data will be collected at any point, however the following procedures will employed:

- 1. We will ask participant the reason for their withdrawal and record that in in their file and in the study database
- We will attempt to meet with the participant for one last visit to collect used/unused patches to determine compliance up to that point, assess and document vitals, and collect any E1G stored or unused urine strips.
- 3. If the participant wishes to withdraw from the intervention conditions, we will ask if they remain willing to complete the self-report surveys, particularly the irritability symptom scale on a daily basis, throughout the remainder of time that would correspond to their 14 study visits as irritability symptomatology is the primary outcome variable.
- 4. If the participant withdraws during or after at least one of the Conditions (TE2 or Placebo), the study gynecologist, [name] will be unblinded and determine if the participant needs the progesterone intervention for uterine protection. If that is determined to be the case, in order to

maintain the blind for research staff and the PI, [name] will be the one to follow the participant and document menses onset, duration, and magnitude associated with the Prometrium.

Criteria for Intervention Discontinuation

An individual will be withdrawn from the study by the investigators under any of the following conditions:

- 1. Inability to tolerate the adhesive in the patches
- 2. If there is indication of psychological distress that impairs function and would warrant treatment. We will monitor the CES-D in real time, on a weekly basis. If the clinical cut point with diagnostic specificity for Major Depressive Disorder (score ≥ 16), [name] will follow-up to assess psychological distress and determine if the participant is able to continue in the study. [name] will determine the next course of action (i.e., participant may continue or will be withdrawn and referred to the UNC Center for Women's Mood Disorders)

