Aim 2a) The two repeated post-treatment EEG measures (theta, beta, ERPs) will be modeled as a function of fixed factors including baseline EEG measures (continuous), Condition status (TE2 or placebo; binary), and order of Condition (binary) in a linear mixed effects model with a random intercept accounting for the within-subject variance. The two-sided Wald test will test the significance of TE2 effects. 2b) Similarly, weekly irritability symptoms (3 weeks/Condition) will be modeled as a function of fixed factors including baseline irritability symptoms (continuous), Condition, and order of Condition in a linear mixed effects model with a random intercept accounting for within-subject variance. Although we hypothesize that E1G variability will predict outcomes in Aim 1 and Condition effects in Aim 2, we will examine E1G levels if analyses do not support variability. In the statistical models described above, all the estimates of treatment effect, along with 95% confidence interval will be reported in the tabulated forms. Whenever multiple testing is used in the analysis described, Benjamini-Hochberg Procedure will be used to adjust for multiple comparison. All the hypothesis tests that yield large p-values will be reported as being inconclusive. To evaluate the robustness of the proposed study, we will perform sensitivity analysis for all the important findings. More specifically, we will repeat all the statistical analysis by excluding some potential outliers that could be influential points. We expect the sensitivity analysis will preserve the direction of original point estimates from full samples. Based on the study design, there will be potential missing data points caused by subject drop-out, and we assume all the missingness will most like to be missing at random (MAR). Since the linear mixed effects model is capable of handling missing values, the analysis plan will not be affected because of missing data.

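### Aim 2b fits several irritability ratings per condition (3 weekly or about 21 daily) with only a random intercept per woman, so positive within-condition correlation makes the TE2 standard error too small

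*Combined protocol and SAP*

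**What the plan says.** Section 8.3, Aim 2b: "weekly irritability symptoms (3 weeks/Condition) will be modeled as a function of fixed factors", namely baseline irritability, Condition and order of Condition, "in a linear mixed effects model with a random intercept accounting for within-subject variance". The model is carried over from Aim 2a, where each EEG measure has one post-treatment value per condition.

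Section 1 (Synopsis, Aim 2 plans) gives the same model for a different record type: "daily irritability symptoms (3 weeks/Condition) will be modeled as a function of fixed factors", again with a random intercept only.

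Other sections do not settle the record type:
- Section 4, Stage 2: "Daily irritability ratings and weekly irritability and general mood ratings are collected throughout all conditions in Stage 2".
- Section 4.3, Table 1 lists "Daily self-reported irritability" as a primary outcome, alongside EEG.
- Section 7.4 schedules a weekly IDAS in Condition 1 but a weekly CES-D in Condition 2. The section 7.1 table marks the IDAS in every week of both.

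Section 3.2 defines the Aim 2b estimand as the difference "between the active TE2 and placebo TE2 conditions in mean irritability symptom severity". Section 7.8 says that "irritability symptomatology is the primary outcome variable".

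The plan has no woman-by-period term, serial residual structure, robust standard error or small-sample degrees of freedom. Its sensitivity analyses cover outliers and missing data only.

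**The concern.** A random intercept per woman implies the same correlation between any two of her ratings, whether from the same three weeks or from different conditions. Ratings from one condition may be more alike than that, for two reasons. A woman may have a better or worse three weeks as a whole (woman-by-period variance), or adjacent ratings may be serially correlated. The model then counts repeated ratings as independent information about TE2.

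The protocol's background makes the first source plausible. Section 2.1 says about 40% of women are susceptible to mood symptoms linked to estrogen change, and that TE2 benefit varied with menopausal stage and stressful events. Women who respond differently to TE2 generate exactly this variance.

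At stake are the confidence interval and test for a primary outcome. Because both record types are named, the reported precision would also depend on which one the analyst picks.

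**Working it through.** **The plan's own figure.** Section 9 gives 85% power for f = 0.25 with N = 30. It does not state alpha, the number of measures k or the correlation ρ. With noncentrality N·k·f²/(1−ρ) and two-sided 0.05:
- k = 3, ρ = 0.5: 30·3·0.0625/0.5 = 11.25, power 84.1%.
- k = 2, ρ = 0.6: 30·2·0.0625/0.4 = 9.375, power 84.1%.
- k = 2, ρ = 0.5: 30·2·0.0625/0.5 = 7.5, power 75.4%.

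So 85% can be approximated under unstated choices. It says nothing about correlation within a condition.

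**Inputs.** N = 30 (section 9). Ratings per condition: m = 3 (section 8.3) or m = 21 (synopsis, 3 weeks × 7 days). Alpha of 0.05 is inferred from the 95% intervals. Assumed, not from the documents: within-woman variance set to 1; woman-by-period share s of 5, 10 or 20%; daily lag-1 correlation of 0 or 0.3.

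**Formulas, without serial correlation.**
- True variance of the TE2 difference: 2·[s + (1−s)/m]/N.
- Variance the planned model reports: 2·σ²/(mN), where σ² is the pooled within-woman mean square, [2N(m−1)(1−s) + (N−1)(ms + 1−s)] / [N(2m−1) − 1].

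**Worked example, s = 20%.**
- Weekly, m = 3: true 2·(0.2 + 0.8/3)/30 = 0.0311. σ² = (96 + 40.6)/149 = 0.917, so reported 2·0.917/90 = 0.0204. True SE / reported SE = 1.24.
- Daily, m = 21: true 2·(0.2 + 0.8/21)/30 = 0.0159. σ² = (960 + 145)/1229 = 0.899, so reported 2·0.899/630 = 0.00285. SE ratio = 2.36.

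For s = 5, 10, 20% the ratios are 1.06, 1.12, 1.24 (weekly) and 1.43, 1.78, 2.36 (daily).

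**Simulated type I error of the planned model (%), no TE2 effect, |z| > 1.96.** Each cell has at least 6,000 trials; Monte Carlo error is at most about 0.5 points.

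| Records | s = 0 | 5% | 10% | 20% |
|---|---|---|---|---|
| Separate weekly ratings | 5.1 | 6.5 | 8.2 | 11.6 |
| Separate weekly, week-to-week correlation 0.3 | 12.7 | 14.0 | 15.3 | 17.9 |
| 7-day means of daily ratings, lag-1 0 | about 5 | 14.0 | 19.9 | 27.2 |
| 7-day means, daily lag-1 0.3 | 5.9 | 11.7 | 16.2 | 22.3 |
| Daily, lag-1 0 | 4.9 | 17.4 | 27.1 | 40.6 |
| Daily, lag-1 0.3 | 14.6 | 24.8 | 32.9 | 43.8 |

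The second row is a separate and stronger assumption: a daily lag-1 of 0.3 implies only 0.3⁷ = 0.0002 at one week.

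**Cross-checks.**
- Fitting the mixed model itself at s = 20% gave 10.7% (weekly, 600 fits) and 33% (daily, only 150 fits, Monte Carlo error about 4 points).
- A t reference with 149 df changes the weekly results by at most 0.4 points.
- If individual TE2 effects vary with an SD of half the residual SD (assumed), the error is 8.7% weekly and 28.9% daily.

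**After the change.** A paired t test on one mean per woman per condition gives 4.6 to 5.2% in every setting. It gives 4.8 to 5.1% when each woman-period loses 0 to 40% of its days at random.

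**The case against.** The strongest reply is that the size rests entirely on assumed values. With no extra correlation the planned model is valid, and with a small period share the damage is small: at 1%, error is 7.9% daily, 5.6% separate weekly and 6.9% for 7-day means. This stands, and it is why the conclusion is conditional.

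Second, the worst figures belong to the synopsis, whereas the detailed analysis section says weekly. For three separate weekly ratings with period variance alone, the inflation is mild to moderate. This also stands. However, Table 1 names the daily rating as the primary outcome, and section 7.4 leaves unclear whether a separate weekly irritability rating exists in Condition 2. The daily case cannot be set aside.

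Third, for 7-day means, serial correlation alone does almost no harm (5.9%, SE ratio 1.02); the problem there needs period variance. That is correct.

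Fourth, the plan does not say that residuals are independent; it leaves their covariance unstated. But a random intercept with nothing added is ordinarily fitted with independent residuals, so following the text literally gives the model examined here.

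Finally, the section 3.2 estimand does not require collapsing to one mean, because a repeated-record model with adequate covariance estimates the same difference. That is fair, and such a model is an acceptable alternative.

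**Conclusion.** The concern holds. As written, Aim 2b understates the TE2 standard error whenever ratings within a condition are positively correlated beyond the woman's overall level, and no other section corrects this.

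The true SE is 1.06 to 1.24 times the reported one for separate weekly ratings with a 5 to 20% period share. It is about 1.4 to 2.5 times for daily ratings over the same shares, with lag-1 correlation of 0 to 0.3. If weekly means 7-day averages, the ratio is 1.25 to 1.76. These ranges rest on assumed variance shares and correlations; only the direction follows from the plan itself.

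The weekly versus daily contradiction is in the text regardless of any assumption. It has to be resolved because it decides which of these ranges applies.

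**What to change.** 1. Name the same record type in section 8.3 and the synopsis. If weekly, state whether it is a separate rating or an average of daily ones, and reconcile section 7.4 with the section 7.1 table on whether the weekly IDAS is collected in both conditions.
2. Make the primary Aim 2b analysis one mean ill-temper score per woman per condition, in the same two-record model as EEG, with a t reference and small-sample degrees of freedom. This estimates the section 3.2 quantity directly and needs no assumption about correlation within a condition.
3. Alternatively, keep the repeated records and add a random woman-by-period intercept, with AR(1) residuals within period for daily data and small-sample degrees of freedom. With missing diary days the result is close to, but not identical with, the condition-mean analysis.

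The cost is SAP wording and a few lines of code, with no change to data collection. Intervals will be wider where the correlation exists. A condition mean weights women equally however many days they completed, and the missing-day check above covers only days lost at random. Power should be restated: for f = 0.25 with two condition means it is 75.4%, 84.1% or 92.7% if a woman's two means correlate at 0.5, 0.6 or 0.7 (assumed), against the stated 85%.

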Duration of Conditions: We have chosen 3-week duration for each Condition based on: 1) The results of co-Investigator, [name], showing maximal effect of TE2 on irritability symptoms within one week; 2) placebo-controlled studies showing TE2 reduces perimenopausal depression symptoms with maximal effects seen in one to three weeks;^{27,28} 3) withdrawal from TE2 increases depressive symptoms within one week in perimenopausal women with histories of perimenopausal depression;²⁹ and 4) clinical experience that maximal efficacy of TE2 for treating perimenopausal depression is evident within two weeks (personal communication, [name]). Thus, the beneficial mood effects of TE2 are rapid and detectable within 3 weeks. With the mean half-life of TE2 equal to 161 mins,³⁰ pharmacokinetic clearance is complete in 13 hours (five half-lives). We will employ a three-week washout window to minimize, if not eliminate, even lagged carryover effects³¹

3. Specific Aims

Alignment of the	Specific Aims with Measures	and Aim-Specific Statistical A	Analysis Plans
Specific Aim	Outcome Measures	Estimands	Statistical Estimators
(1) Determine baseline relationships:			
a) E1G variability and irritability symptoms	-Every-other-day baseline E1G measurements -weekly irritability score	-Standard deviation of 14 E1G measurements -average of 4 weekly irritability (IDAS) scores	Model-based estimates, all with 95% C.I., regression coefficients
b) E1G variability and neural oscillations	-E1G standard deviation -frontal theta (dB) during threat, parietal beta (dB) during frustration	-E1G standard deviation -average event-related theta (dB) during Dot Probe Paradigm/ average event-related beta (dB) during Affective Posner Paradigm	Model-based estimates, all with 95% C.I., regression coefficients
c) irritability symptoms and neural oscillations	-weekly irritability score -frontal theta, parietal beta	-average of 4 weekly irritability scores -frontal theta (dot probe), parietal beta (Affective Posner Paradigm)	Model-based estimates, all with 95% C.I., regression coefficients

(2) Determine effect of TE2 administration on:

a) neural oscillations -Event-related frontal

-Event-related frontal - Frontal theta during dot theta and parietal beta probe/Parietal beta during Affective Posner

Paradigm

Model-based estimates, all with

95% C.I.

b) irritability symptoms

-irritability symptoms

-IDAS irritability symptoms

Model based estimates

3.1. Aim 1

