We will administer the Center for Epidemiologic Studies Depression Scale (CES-D) weekly throughout the study. The total CES-D score may range from 0–60 reflecting level of depressive symptoms. A clinical cutpoint for Major Depressive Disorder has been established (score ≥16). We will monitor the weekly CES-D submissions and use scores at these levels to warrant follow-up by [name] or [name] to assess psychological distress and determine if the participant is able to continue in the study.

The **5-item ill temper scale of the IDAS will be the primary measure of irritability** and will be used at enrollment to ensure at least moderate levels of irritability, and daily to examine associations with E1G variability and EEG measures. **We will require an ill temper score of >10** (range 5-25), consistent with [name] preliminary data showing perimenopausal depressed women with levels of 11 on this scale are responsive to TE2.

The Behavioral Inhibition/Behavioral Activation Systems (BIS/BAS) 38 (RDoC Matrix) is comprised of 20 items. Respondents answer with a 1 – 4 scale (the statement is 1 = very true for me vs. 4 = very false for me). Lower scores reflect more agreement with the statement. This survey has five subscales that assess:

- 1) Behavioral activation (BAS, impulsivity) five item subscale with scores ranging from 5 20
- 2) Reward Responsiveness five item subscale with scores ranging from 5 20
- 3) Fun Seeking four item subscale with scores ranging from 4 16
- 4) Behavioral inhibition (BIS, anxiety) seven item subscale with scores ranging from 7 28.

We also include the 5-item $\frac{\text{Frustrative Non-reward Responsiveness Subscale}}{\text{Mon-reward Responsiveness Subscale}}$ (RDoC Matrix) to quantify approach motivation following FNR. This subscale is imbedded in the BIS/BAS instrument with lower scores reflecting greater frustration to non-reward. The scores range from 5-20.

We will administer these scales immediately before the two EEG tasks designed to activate threat/anxiety (the Dot Probe task) and frustration to non-reward (the Affective Posner Paradigm) at baseline Visit 4 and again at end of Condition 1 (Visit 7) and Condition 2 (Visit 13).

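### Aim 2b models daily irritability in the Synopsis but weekly irritability in Section 8.3, and the choice changes the primary test

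*Combined protocol and SAP*

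**What the plan says.** The response for Aim 2b is stated twice.

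- Synopsis, Aim 2 Plans: "daily irritability symptoms (3 weeks/Condition) will be modeled as a function of fixed factors including baseline irritability symptoms (continuous").
- Section 8.3, Aim 2b: "weekly irritability symptoms (3 weeks/Condition) will be modeled as a function of fixed factors including baseline irritability symptoms (continuous").

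The rest of each sentence is nearly the same: Condition and order as further fixed factors, and a random intercept per woman.

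Other places bear on which is meant.

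- Section 4.3, Table 1 lists "Daily self-reported irritability" at Visits 1 to 13, for all aims, as a primary outcome. Sections 7.8 and 7.9 also call irritability the primary outcome variable.
- Section 4, Stage 2: "Daily irritability ratings and weekly irritability and general mood ratings are collected throughout all conditions in Stage 2". The Table of Events has separate rows for the IDAS and for daily irritability, both marked in both Conditions.
- Section 7.4 lists a weekly IDAS for Condition 1, but a weekly CES-D for Condition 2.
- In the Section 3 table, the Aim 2b row says only "IDAS irritability symptoms". The Section 3.2 estimand compares the "conditions in mean irritability symptom severity". Neither gives a frequency.
- The same conflict appears for Aim 1. The Section 3 table uses the "average of 4 weekly irritability (IDAS) scores" for Aim 1a and weekly scores again for 1c, whereas the Synopsis measures baseline irritability daily.

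**The concern.** The section that specifies the test and the sections that name the outcome give different response variables for a primary outcome. No definition links them: nowhere is the weekly value said to be an average of that week's daily ratings.

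Either version could be defended from the text after the data are seen. A borderline result could then be conclusive under one version and, in the plan's own term, inconclusive under the other. The Benjamini-Hochberg step does not cover this, because only one version would be reported.

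**Working it through.** **The plan's own figure.** Section 9 claims, with N = 30, over 95% power at f = 0.55 and 85% at f = 0.25 for irritability. For a two-condition repeated-measures F test, λ = N·m·f²/(1−ρ) with m = 2.

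- f = 0.55: 98.4% at ρ = 0 and above 99.9% at ρ = 0.5. The claim reproduces.
- f = 0.25: 46.5% at ρ = 0, 75.4% at 0.5, 84.1% at 0.6 and 92.7% at 0.7. About ρ = 0.61 is needed for 85%.

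Section 9 gives no ρ and no number of repeated measures. The 85% can be neither confirmed nor called wrong, and it does not show whether daily or weekly data were intended.

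**Inputs.** 30 completers (Section 5.1). Three weeks per Condition, so 30 × 2 × 21 = 1260 daily rows or 30 × 2 × 3 = 180 weekly rows. Random intercept and Wald test (Section 8.3). Two-sided 5% is assumed from the 95% intervals, as alpha is not stated. The documents give no correlations, so ranges are used.

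**Reading A: the weekly score is a separate rating.** Two one-sample t tests were simulated on 30 within-woman differences, with correlation r between the two contrasts.

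| r | At least one significant, no effect | Exactly one significant, 85% power each |
|---|---|---|
| 0.5 | 9.2% | 19% |
| 0.7 | 8.4% | 14% |
| 0.8 | 7.8% | 12% |
| 0.9 | 7.1% | 9% |

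**Reading B: the weekly score is the mean of seven daily ratings.** With complete data the TE2–placebo estimate is identical. The standard error is not, because a random intercept alone treats all rows within a woman as equally correlated. Take AR(1) day-to-day errors with variance σ² and correlation ρ, and no subject-by-condition variance. The true variance of a 21-day mean is (σ²/21)·g, with g = 1 + 2Σ(1 − k/21)ρᵏ for k = 1 to 20.

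At ρ = 0.5, g = 2.810:

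- Daily rows: the expected residual variance is 0.9544σ². The ratio of true to model variance is 2.810/0.9544 = 2.944. Then 1.96/√2.944 = 1.142, a two-sided tail of about 25%.
- Weekly rows: the true variance of the Condition mean is 2.810σ²/21 = 0.1338σ². The expected residual variance is 0.3364σ², so the model uses 0.3364σ²/3 = 0.1121σ². The ratio is 1.193. Then 1.96/√1.193 = 1.794, a tail of about 7%.
- One mean per Condition: true and model variances agree. Using 1.96 with 29 degrees of freedom gives about 6%.

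Simulation of the planned test (3000 runs per cell) agrees:

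| ρ | Daily rows | Weekly rows | One mean per Condition |
|---|---|---|---|
| 0 | 4.9% | 5.1% | 5.9% |
| 0.3 | 14.2% | 5.9% | 5.6% |
| 0.5 | 24.9% | 7.0% | 5.4% |
| 0.7 | 38.7% | 10.5% | 6.3% |

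With a subject-by-condition SD of 0.3 (in daily residual SDs), the rates are 23.7% to 47.0% for daily rows and 13.1% to 17.8% for weekly rows. One mean per Condition stays at 5.5% to 6.4%.

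**The case against.** The strongest defence is that weekly is loose wording for a weekly summary of the daily ratings. Much of the text fits this. The Synopsis separates weekly mood ratings from daily ill temper ratings. Section 4.3 gives the full IDAS at enrollment and makes the CES-D the weekly form, as does Section 12.3. The Table of Events has no CES-D row, so its IDAS row may be a mislabel. This reading is plausible, and under it the Reading A figures do not apply. It does not settle the matter: Section 4 speaks of weekly irritability ratings as well as daily ones, and Reading B shows that the two tests still differ.

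Some stronger readings are tempting but not supported.

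- A reader might infer that Section 3 makes Aim 2b weekly. Its weekly wording covers only Aims 1a and 1c. Section 8.3 alone makes the Aim 2b response weekly.
- A reader might count the Section 4.3 text on the ill temper scale as naming daily for Aim 2b. It says the scale is "used at enrollment to ensure at least moderate levels of irritability, and daily to examine associations with E1G variability and EEG measures", which does not mention the TE2–placebo contrast.
- A reader might infer from Section 7.4 that no weekly IDAS exists in Condition 2, leaving about 15 v 15 women and 26% power at d = 0.5. Section 4 and the Table of Events contradict that reading, and Section 7.4 has evident copying slips: it places the Condition 1 and 2 laboratory visits at the end of baseline week 4. The 26% also leaves out the baseline covariate. Section 7.4 needs reconciling, but the within-woman contrast is not shown to be lost.

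**Conclusion.** The contradiction holds. The Synopsis and Section 8.3 give different responses for Aim 2b, and nothing in the documents resolves it. It matters under either meaning of weekly. As a separate rating, it opens a second primary test and raises the chance of at least one significant result from 5% to about 7% to 9%. As a mean of daily ratings, it leaves the estimate unchanged with complete data but moves the false-positive rate: roughly 5% to 39% for daily rows against 5% to 10% for weekly rows, over day-to-day correlations of 0 to 0.7 with no subject-by-condition variance. All these sizes rest on assumed correlations and an assumed two-sided 5% level. They show how far the choice can matter, and do not predict this trial's error rate.

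**What to change.** State one Aim 2b primary response in both the Synopsis and Section 8.3: each woman's mean daily ill temper rating over each three-week Condition, one value per woman per Condition. This matches the Section 3.2 estimand. Do not simply replace weekly with daily in Section 8.3. Entering 21 daily values into the unchanged random-intercept model selects the more inflated test.

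Use the mean of the baseline daily ratings as the baseline covariate. Section 8.1 now gives only a five-item sum, with no day or averaging rule. Use the same baseline mean in the Aim 1a and 1c rows of Section 3. Reconcile Section 7.4 with Section 4 and the Table of Events on whether a weekly IDAS is collected in both Conditions, and label any weekly IDAS analysis as supportive. Settle this before unblinding.

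The cost is wording, with no new data or visits. The weekly score can no longer carry the primary claim. The confidence interval may also be wider than the one from daily rows: at ρ = 0.5 the standard error is about √2.944 = 1.7 times as large, because the daily-row model understates it.
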